Note: Compared with the control group, $P < 0.05$

Table 5 Comparison of curative effect of TCM syndromes between two groups (%)

Group	Chest pain			
	ME	effective	invalid	TER
Test (n=80)	26 (32.50)	45 (56.25)	9 (11.25)	71 (88.75)
Control (n=80)	19 (23.75)	32 (40.00)	29 (36.25)	51 (63.75)

Group	Chest tightness			
	ME	effective	invalid	TER
Test (n=80)	26 (32.50)	46 (57.50)	8 (10.00)	72 (90.00)
Control (n=80)	28 (22.50)	35 (43.75)	27 (33.75)	53 (66.25)

Group	pant			
	ME	effective	invalid	TER
Test (n=80)	24 (32.50)	48 (60.00)	8 (10.00)	72 (90.00)
Control (n=80)	18 (22.50)	34 (42.50)	28 (35.00)	52 (65.00)

Group	palpitation			
	ME	effective	invalid	TER
Test (n=80)	22 (27.50)	48 (60.00)	10 (12.50)	70 (87.50)
Control (n=80)	17 (21.25)	34 (42.50)	29 (36.25)	51 (63.75)

Note: Compared with the control group, $p < 0.05$

Table 6 Comparison of ECG changes after treatment between two groups (%)

Test (n=80)	18 (22.50)	39 (48.75)	23 (28.75)	57 (71.25)
Control (n=80)	16 (20.00)	35 (43.75)	29 (36.25)	51 (63.75)

Note: Compared with the control group, $P < 0.05$

Studies have confirmed that Xinnaoning Capsule has a good clinical effect on angina pectoris patients after coronary artery stent implantation by improving myocardial microcirculation, promoting the opening of collateral circulation, inhibiting platelet aggregation, lowering blood lipid and stabilizing platelet. There were no significant changes in ECG, blood pressure and heart rate before and after treatment, and no obvious adverse reactions during treatment, suggesting that the drug is safe.

For many years after Xinnaoning capsule was put on the market, no adverse reactions were recorded in the literature. This experiment completes the clinical trial of Xinnaoning Capsule in treating chronic stable angina pectoris (Qi stagnation and blood stasis syndrome), and objectively evaluates its clinical efficacy and safety.

2. Experimental purpose

To evaluate the efficacy and safety of Xinnaoning Capsule in the treatment of chronic stable angina pectoris (Qi stagnation and blood stasis syndrome)

3. Experimental design

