10.2.3 Statistical analysis content

(1) CDAS3.0 statistical software will be used for statistical analysis.

(2) The main therapeutic data set was FAS analysis population, and the therapeutic PPS population was also analyzed.

(3) Except for the superiority test of the main therapeutic indicators, all other statistical tests are carried out by bilateral test, and the difference of P value less than or equal to 0.05 will be considered statistically significant.

(4) The measurements of each visit in different treatment groups will be described by means of standard deviation. Compared with the baseline values at the time of admission, paired t-test was used to compare the differences between before and after admission. Variance analysis was used to compare the changes before and after treatment in each group.

(5) Frequency (constituent ratio) was used to describe the counting data of each visit in different treatment groups. 2 test or non-parametric test were used to test the changes before and after treatment in each group.

(6) Comparability analysis: Comparing demographic data and other basic value indicators to measure the comparability between the two groups.

(7) Compliance analysis: Compare the two groups of patients whether to use the research drugs on time and in quantity, not using the drugs prohibited in the program.

(8) Abscission analysis: χ^2 test will be used to compare the total abscission rate and the abscission rate due to adverse events in each group.

(9) Equilibrium analysis of basic values: using variance analysis or 2 test to compare demographic data and other basic value indicators to measure the two groups of equilibrium.

(10) Effectiveness analysis: PPS and FAS were used to analyze the main indicators and global indicators, and CMH test considering the central effect was used to analyze the efficacy of the two groups. The main effect indicators were selected to treat 12 weeks of angina symptoms, and the placebo was used as the control for statistical test.

(11) Analysis of factors affecting efficacy: If there are significant correlative factors affecting efficacy, these factors should be considered as covariance analysis or logistic regression analysis when comparing the efficacy of the two groups. Detailed list of combined medication is required.

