(12) Safety analysis: 2 test was used to compare the incidence of adverse events in the two groups, and list the adverse events in the study; analysis of the normal/abnormal changes of laboratory results before and after the study and the relationship between abnormal changes and research drugs.

11. Quality Control and Guarantee of Clinical Trials

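### Adverse events and adverse-event dropout are compared between arms by a chi-square P-value alone; a risk difference with a 95% interval would be more informative for a safety purpose

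*Protocol*

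**What the plan says.** Section 2 gives the purpose as "To evaluate the efficacy and safety of Xinnaoning Capsule in the treatment of chronic stable angina pectoris", so safety stands beside efficacy.

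Section 10.2.3 then fixes how adverse events are compared:

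- Item (12): a chi-square test (the chi symbol was lost when the text was read from PDF). The item reads "2 test was used to compare the incidence of adverse events in the two groups". It also asks for a listing of the events, for "analysis of the normal/abnormal changes of laboratory results before and after the study" and for the relation of abnormal changes to the drug.
- Item (8): a chi-square test to "compare the total abscission rate and the abscission rate due to adverse events in each group".
- Item (3) sets the threshold for everything apart from the superiority test of the primary indicator: "all other statistical tests are carried out by bilateral test, and the difference of P value less than or equal to 0.05 will be considered" (that is, deemed significant).

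Confidence intervals appear in section 10.2.1(5), in a general list of descriptive statistics that is not linked to any safety contrast. Section 3.2 sets the sample size on the angina response rate only. No adverse-event rate, safety margin or safety power is given.

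**The concern.** A significance test asks whether the data exclude zero difference. A safety purpose needs to know how large an excess of harm the data still allow. When events are few, the first question is usually answered "no", and that answer leaves the second open. The background in section 1 reports no recorded adverse reactions after marketing, so few drug reactions are presumably expected, and that is where the test is weakest.

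At stake is how informative the safety result will be. If the P-value is the only between-arm summary, a reader cannot tell a trial that excludes a material excess from one that was simply too small to see it.

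**Working it through.** **Inputs from the protocol.** 120 per arm, 1:1 (sections 3.1 and 3.2). Two-sided test at 0.05 (10.2.3 item 3). The safety set is everyone who took at least one treatment after randomization (10.1), so close to 120 per arm.

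**Inputs assumed.** All adverse-event rates. The protocol gives none, so a range is shown.

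**The plan's own sample size.** With the printed formula, in percentages:

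[67.5 × 32.5 + 84.3 × 15.7] / (84.3 − 67.5)² × f = (2193.75 + 1323.51) / 282.24 × f = 12.462 × f.

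With the tabled f = 7.9 (two-sided 0.05, 80% power) this is 98.4, as stated. With the unrounded f = 7.849 it is 97.8. The figure reproduces and rests on efficacy alone.

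**Power of the adverse-event test.** Both binomials were enumerated with n = 120 per arm. The probabilities of all outcomes were summed where the uncorrected Pearson statistic

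(x₁/n − x₂/n)² / [p̄(1 − p̄) × 2/n], with p̄ = (x₁ + x₂)/(2n),

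reaches 3.84, the 5% point of chi-square on 1 df.

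| Assumed rates | Exact power |
|---|---|
| 1% v 2% | 7% |
| 2% v 4% | 13% |
| 2% v 6% | 34% |
| 5% v 10% | 32.5% |
| 10% v 20% | 59% |
| 5% v 15% | 76% |
| 15% v 30% | 80% |

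The normal approximation gives 31% for 5% v 10% and 93% for 20% v 40%. With a Yates correction or Fisher's exact test, 5% v 10% falls to 22%. With 96 per arm (20% lost) the uncorrected test has 26%.

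**What the P-value leaves out.** Take an illustrative result of 12/120 on test and 6/120 on control.

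- Difference: 10% − 5% = 5 points.
- Pooled rate: 18/240 = 7.5%. Standard error: √(0.075 × 0.925 × 2/120) = 0.0340. So z = 0.05/0.0340 = 1.47 and P = 0.14.
- Wilson 95% limits: 5.8% to 16.7% (test) and 2.3% to 10.5% (control).
- Newcombe lower limit: 5.0 − √[(10.0 − 5.8)² + (10.5 − 5.0)²] = −1.9 points.
- Newcombe upper limit: 5.0 + √[(16.7 − 10.0)² + (5.0 − 2.3)²] = +12.2 points.

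The test would report no significant difference, yet the data remain compatible with an excess of about 12 points.

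**Sparse counts.** With equal arms, the expected number of events per arm is half the total. Fewer than 10 events in all puts it below 5, the usual point for changing to Fisher's exact test. That is likely for serious events and for discontinuations due to adverse events.

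**The case against.** The strongest reply is that the protocol contains no error here. Four parts of it stand.

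- **No rule equates non-significance with safety.** A reader might infer one from section 1, where earlier trials are summarised with "There were no significant changes in ECG, blood pressure and heart rate before and after treatment" and the drug is then called safe. Those sentences describe before-and-after changes in vital signs and ECG in other studies. They report no between-arm adverse-event test and set no analysis rule for this trial. Item (3) only defines when a P-value counts as significant.
- **The chi-square test is not the whole safety evaluation.** A reader might infer that it is. Item (12) also lists events and analyses laboratory shifts, and section 7.1.2 grades severity and causality and defines an adverse-reaction incidence. The point is limited to the between-arm comparison of event incidences.
- **The rates are assumed.** It would be wrong to say that the test generally misses a doubling or tripling: it finds 5% v 15% about three times in four and 15% v 30% about four times in five. Section 7.1.1 defines adverse events broadly, so a control rate above 10% cannot be excluded.
- **Low power for uncommon events is normal** in a trial sized on efficacy and contradicts nothing stated.

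It can also be said that intervals are SAP detail, and an SAP that is not shown may supply them. That has weight, but items (8) and (12) do name the comparison, and what they name is a significance test. The reply reduces the point to an improvement without removing it.

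**Conclusion.** The point holds as a cheap improvement to the analysis, and not as an error in the protocol. The chi-square test is the only comparison that items (8) and (12) name for adverse-event incidence and adverse-event dropout, and they attach no estimate or interval to it. At 120 per arm its power ranges from 7% (1% v 2%) to about 80% (15% v 30%) over the rates tabulated. All of these rates are assumptions, and the figures use the uncorrected Pearson test. If events prove uncommon, a non-significant P-value alone will say little about excess harm. If they prove common, the test performs reasonably, but the interval would still be the more useful summary.

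**What to change.** In section 10.2.3 items (8) and (12):

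1. Make the main between-arm summary the risk difference (test minus control) with a two-sided 95% confidence interval, by Newcombe or Miettinen-Nurminen. Apply it to all adverse events, adverse reactions, serious adverse events and discontinuation due to adverse events.
2. Keep the P-value as supportive, with Fisher's exact test where expected counts are below 5.
3. State that a non-significant P-value will not be taken as evidence of safety.

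Do not write a detectable excess or a safety power into the protocol, because any such figure would depend on rates that the protocol does not have.

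The cost is a sentence or two and an extra column in the adverse-event tables, with no new patients or data. The downside is that the safety statement will look less favourable, because wide intervals will be visible.

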11.1 Records of clinical trials

Researchers should fill in all cases according to the design requirements of the "case report form" one by one. Research medical records and case report forms shall be used as original records and shall not be changed. When making any corrections,

the original record shall not be blackened. Only a horizontal line can be drawn at the amendment and the reasons can be explained by adding a description. The physician participating in the clinical trial shall sign and date it.

Laboratory data in clinical trials should be recorded, and original reports (or copies) should be glued to the medical records of the study. Data that are significantly higher or beyond clinical acceptability should be verified and explained by the physician participating in the clinical trial.

All medical records and case reports should be filled in with black or blue-black signature pens. Ball pens, pens or pencils are prohibited.

11.2 Management of experimental drug use

All drugs should be kept in the scientific pharmacy of the hospital and designated special persons to be responsible for the preservation, distribution, recovery and return of the drugs. For the cases of withdrawal and missing visits, the experimental drugs should be recovered. At the same time, we should establish the Record of Use of Drugs in Clinical Trials, which includes the date of issuance of drugs, the names of subjects, the number of drugs issued, the date of recovery, the number of drugs recovered, the signature of the dispenser and the signature of the drug collector.

11.3 Training Researchers

Before the start of clinical trials, the personnel participating in clinical trials should be trained in a unified way so that researchers can fully understand the specific connotations of the clinical trial program and its indicators; the quantification criteria of symptoms and signs are basically the same; the description of conscious symptoms should be objective, and should not be induced or prompted; and the prescribed objective indicators should be carried out according to the time points and methods prescribed by the program. Check; Familiar with the recording methods of case history and CRF; pay attention to observe adverse reactions or unexpected side effects, and follow up observation.

11.4 Measures to Improve Observation Consistency

1) Qualification examination of researchers participating in clinical trials: They must have the professional expertise, qualification and ability of clinical trials. After qualification examination, they are determined and the personnel requirements are relatively fixed.

2) Researchers should verify significant deviations or data beyond acceptable limits and make necessary explanations by the researcher.

3) Each test item must indicate the unit of measurement used.

4) Each clinical research unit should appoint a special person to regularly check the progress of clinical trials and carefully verify the data and records.

5) If necessary, the bidding unit will organize a mid-term clinical meeting to check the previous work, analyze the problems found in the clinical trial process and put forward the rectification.

11.5 Laboratory Quality Control Requirements

Standard operating procedures and quality control procedures should be established in laboratories. When the main indicators may be subjectively affected, a consistency test is needed.

Each testing unit shall provide "normal range of laboratory inspection" for its own unit. If there is any change in the test, additional explanation should be provided in time. Effective measures should be taken to correct the differences in the results of laboratory tests or the range of normal reference values.

11.6 Surveillance of clinical trials

Qualified inspectors appointed by the applicants will regularly visit the test centers during the trial period to ensure that the rights and interests of the subjects in the clinical trials are guaranteed, that the data recorded and reported in the trials are accurate and complete, and that the trials follow the approved programs, drug clinical trial management norms and relevant regulations.

The inspector is required to have direct access to source documents (original documents, data and records). Direct contact includes allowing examination, analysis, and verification of important records and reports for any evaluation of clinical trials.

Researchers should be able to contact the Ombudsman by telephone at any time for discussion.

12. Ethical principles

Before the clinical trial is officially started, it must be discussed, revised and signed by the researcher and the applicant (i.e. this scheme), which can be submitted to the Ethics Committee for approval before the trial can be started. If problems arise in the actual implementation of clinical trials and need to be revised, please submit to the applicants that, after consultation and discussion by the multi-center coordinating committee, the responsible unit of clinical trials should revise the scheme and submit it in writing to the applicants and the experimental units for signature and approval, and then to the Ethics Committee for approval; if it is found that the drug used in the trial is involved, it should be carried out after approval by the ethics committee.

Important new material must be revised in writing and sent to the Ethics Committee for approval, and the subject's consent will be obtained again.

Before the start of a clinical trial, researchers must provide the subjects with detailed information about the nature of the trial, the purpose of the trial, the potential benefits and risks, alternative therapies available, and the rights and obligations of the subjects in line with the Helsinki Declaration, so that the subjects can fully understand and consent and sign the informed consent. Bed test. Every subject should leave detailed contact address, telephone, identity certificate and other information. At the same time, the doctor should leave his own contact telephone to the subject so that the subject can find the doctor whenever the condition changes. This is also conducive to the doctor to keep abreast of the change of the condition, reminding the subject to return to the doctor in time to avoid missing the visit.

13. Data preservation

Researchers must keep the original data of each subject, including all medical records and visiting records (including demographic and medical information, laboratory data, electrocardiogram, other examination or evaluation results), and a signed consent form.

Case report forms are written in carbon-free duplicate triple format. After data entry is completed, the applicants, clinical trial units and responsible units of clinical trials are filed separately.

All test data must be kept for 5 years after the end of the test. If required by existing regulations or agreements with bidders, such information should be kept for a longer period of time. The applicant or his agent will notify the researcher in writing of the deadline when the information no longer needs to be kept. If the research unit adjusts the location of the documents, the researcher shall notify the applicant or his agent in writing.

14. Modification of the scheme

After approval by the ethics committee, if there are significant changes in the implementation process, the main researchers in charge of clinical trials will write the "revised instructions" and sign them. At the same time, they need to report to the Ethics Committee for approval before they can be implemented. If no principled modification is made, the principal investigators, statisticians and bidders of the responsible unit of clinical trial shall discuss and decide together, and notify other participating units.

15. Organization and Management of Tests

2) Exercise after noon is better: Angina pectoris, myocardial infarction and sudden death often occur from 5 am to 11 noon due to high tension of coronary artery in the morning and morning. The most suitable time for subjects with coronary heart disease is 7-9 pm. If some people are used to exercise in the morning, they should drink a large glass of water on an empty stomach before exercise.

3) Controlling the amount of motion;

4) No competitive sports activities;

5) Step by step and persevere;

6) inappropriate activities before and after meals: in principle, no exercise within 2 hours after meals, no meals or strong tea within 1 hour after exercise;

7) Don't take a bath immediately after exercise.

8) Prepare and relax before exercise;

9) Be in a good mood;

10) Avoid direct sunlight and windward exercise;

2. When can coronary heart disease subjects not exercise?

1) In quiet conditions, angina attacks often occur, and all kinds of coronary heart disease can not be controlled by treatment.

2) mild activity, i.e. palpitation, shortness of breath, wheezing or accompanied by cardiac insufficiency;

3) those who have serious arrhythmia, tachycardia, bradycardia, atrioventricular block and can not be controlled by medication;

4) Acute infection subjects;

5) accompanied by severe hypertension;

6) Patients with diabetes mellitus and uncontrolled condition after treatment;

- 7) Severe stenosis of three coronary arteries ranged from 80% to 90%.
 - 8) Myocardial infarction with pericarditis and myocarditis;
 - 9) Those with obvious myocardial ischemia, thrombophlebitis or recent history of embolism.
3. Notices for exercise of subjects with coronary heart disease:
- 1) Avoid training in bad weather, training before noon or afternoon in winter and early morning or evening in summer.
 - 2) When walking, avoid windward, upper and lower steps and explosive force;
 - 3) Avoid excessive exertion of upper limbs, especially lifting weights;
 - 4) Avoid emotional excitement, tension and anger. In such cases, stop exercising and learn to relax.
 - 5) When you feel tired, chest pain, dizziness, shortness of breath, whatever you are doing, you should stop and rest immediately.
 - 6) Do not exceed the target heart rate prescribed by the doctor.
 - 7) insist on taking medicine according to doctor's advice. Do not randomly add or subtract prescribed medicines by doctors; if some acute diseases occur, such as colds, diarrhea, etc., stop training.

4. Motion Method

1) Type of exercise: Walking, jogging, cycling or fitness bike, swimming and other sports are more suitable for coronary heart disease subjects. Because these sports belong to low to moderate intensity sports, mainly endurance sports. The energy metabolism of these exercises is mainly in the form of aerobic metabolism, so it is called "aerobic exercise" in medicine. Long-term exercise can improve the body's oxygen carrying capacity and cardiopulmonary function.

2) Volume of exercise: It is mainly composed of intensity, duration and frequency of exercise, which can be coordinated with each other.

① The intensity of exercise is an important index to ensure that the effect of exercise is achieved without causing danger.

Exercise intensity can be divided into three levels (low intensity, medium intensity and high intensity). It is measured by the amount of oxygen consumption during exercise. The greater the oxygen consumption, the greater the intensity of exercise. However, because it is difficult to measure oxygen consumption in clinical practice, heart rate is often used as the most practical index to measure exercise

intensity in actual exercise. The subjects only needed to count their own pulse for 15 seconds, multiplied by 4, to get a heart rate per minute. But this method is only suitable for subjects without arrhythmia. The highest heart rate at low and moderate intensity exercise was 100 beats per minute and 100-120 beats per minute respectively.

Generally speaking, subjects with coronary heart disease can exercise at low to moderate intensity.

② Number of exercises: exercise 3 to 5 times a week to achieve the purpose of calcination.

③ Exercise time: 30-40 minutes each time, including 5-10 minutes of preparation exercise; 15-20 minutes of formal exercise, during which the expected heart rate can be achieved; 5-10 minutes of finishing exercise.

3) Generally speaking, the slight increase of systolic blood pressure (systolic blood pressure does not exceed 20 mmHg) and the increase of heart rate (the ratio of heart rate to activity does not exceed 20 beats/min or the maximum heart rate does not exceed 120 beats/min) after exercise are normal reactions. But if there are shortness of breath, angina pectoris, arrhythmia, dizziness, nausea, paleness and long-term fatigue, insomnia and other discomforts after the activity, it is suggested that this exercise should be reduced or suspended in the next exercise.
